9. STUDY CONDUCT CONSIDERATIONS

9.1. Posting of Information on Publicly Available Clinical Trial Registers

Study information from this protocol will be posted on publicly available clinical trial registers before enrolment of subjects begins.

9.2. Regulatory and Ethical Considerations, Including the Informed Consent Process

Prior to initiation of a study site, GSK will obtain favourable opinion/approval from the appropriate regulatory agency to conduct the study in accordance with ICH Good Clinical Practice (GCP) and applicable country-specific regulatory requirements.

The study will be conducted in accordance with all applicable regulatory requirements.

The study will be conducted in accordance with ICH GCP, all applicable subject privacy requirements, and the ethical principles that are outlined in the Declaration of Helsinki 2008, including, but not limited to:

- Institutional Review Board (IRB)/Independent Ethics Committee (IEC) review and favourable opinion/approval of study protocol and any subsequent amendments.
- Subject informed consent.
- Investigator reporting requirements.

GSK will provide full details of the above procedures, either verbally, in writing, or both.

Written informed consent, as governed by local regulations, must be obtained from each subject prior to participation in the study. It is anticipated that some subjects will have some or all of the study qualification procedures done as part of routine care outside of the auspices of this study. The data from these procedures may be used to assess eligibility and recorded in the eCRF as long as the subject has signed the informed consent.

In approving the clinical protocol the IEC/IRB and, where required, the applicable regulatory agency are also approving the optional assessments e.g., genetic assessments

described in [Appendix 4](#), unless otherwise indicated. Where permitted by regulatory authorities, approval of the optional assessments can occur after approval is obtained for the rest of the study. If so, then the written approval will clearly indicate approval of the optional assessments is being deferred and the study, except for the optional assessments, can be initiated. When the optional assessments are not approved, then the approval for the rest of the study will clearly indicate this and therefore, the optional assessments will not be conducted.

9.3. Quality Control (Study Monitoring)

In accordance with applicable regulations, GCP, and GSK procedures, GSK monitors will contact the site prior to the start of the study to review with the site staff the protocol, study requirements, and their responsibilities to satisfy regulatory, ethical, and GSK requirements. When reviewing data collection procedures, the discussion will include identification, agreement and documentation of data items for which the CRF will serve as the source document.

GSK will monitor the study to ensure that the:

- Data are authentic, accurate, and complete.
- Safety and rights of subjects are being protected.
- Study is conducted in accordance with the currently approved protocol and any other study agreements, GCP, and all applicable regulatory requirements.

The investigator and the head of the medical institution (where applicable) agrees to allow the monitor direct access to all relevant documents.

9.4. Quality Assurance

To ensure compliance with GCP and all applicable regulatory requirements, GSK may conduct a quality assurance assessment and/or audit of the site records, and the regulatory agencies may conduct a regulatory inspection at any time during or after completion of the study. In the event of an assessment, audit or inspection, the investigator (and institution) must agree to grant the advisor(s), auditor(s) and inspector(s) direct access to all relevant documents and to allocate their time and the time of their staff to discuss the conduct of the study, any findings/relevant issues and to implement any corrective and/or preventative actions to address any findings/issues identified.

9.5. Study and Site Closure

The study will complete when the last subject randomized completes the 12-week treatment period and the 12-week observational follow-up (Week 24 visit).

Upon completion or termination of the study, the GSK monitor will conduct site closure activities with the investigator or site staff (as appropriate), in accordance with applicable regulations, GCP, and GSK Standard Operating Procedures.

GSK reserves the right to temporarily suspend or terminate the study at any time for reasons including (but not limited to) safety issues, ethical issues, or severe non-compliance. If GSK determines that such action is required, GSK will discuss the reasons for taking such action with the investigator or head of the medical institution (where applicable). When feasible, GSK will provide advance notice to the investigator or head of the medical institution of the impending action.

If a study is suspended or terminated for **safety reasons**, GSK will promptly inform all investigators, heads of the medical institutions (where applicable), and/or institutions conducting the study. GSK will also promptly inform the relevant regulatory authorities of the suspension/termination along with the reasons for such action. Where required by applicable regulations, the investigator or head of the medical institution must inform the IRB/IEC promptly and provide the reason(s) for the suspension/termination.

9.6. Records Retention

Following closure of the study, the investigator or head of the medical institution (where applicable) must maintain all site study records (except for those required by local regulations to be maintained elsewhere) in a safe and secure location. The records must be easily accessible when needed (e.g., for a GSK audit or regulatory inspection) and must be available for review in conjunction with assessment of the facility, supporting systems, and relevant site staff.

Where permitted by local laws/regulations or institutional policy, some or all of the records may be maintained in a format other than hard copy (e.g., microfiche, scanned, electronic); however, caution must be exercised before such action is taken. The investigator must ensure that all reproductions are legible and are a true and accurate copy of the original. In addition, they must meet accessibility and retrieval standards, including regeneration of a hard copy, if required. The investigator must also ensure that an acceptable back-up of the reproductions exists and that there is an acceptable quality control procedure in place for creating the reproductions.

GSK will inform the investigator of the time period for retaining the site records in order to comply with all applicable regulatory requirements. The minimum retention time will meet the strictest standard applicable to a particular site, as dictated by local laws/regulations, GSK standard operating procedures, and/or institutional requirements.

The investigator must notify GSK of any changes in the archival arrangements, including, but not limited to archival of records at an off-site facility or transfer of ownership of the records in the event that the investigator is no longer associated with the site.

9.7. Provision of Study Results to Investigators, Posting of Information on Publicly Available Clinical Trials Registers and Publication

Where required by applicable regulatory requirements, an investigator signatory will be identified for the approval of the clinical study report. The signatory investigator will be provided reasonable access to statistical tables, figures, and relevant reports and will have

the opportunity to review the complete study results at a GSK site or other mutually-agreeable location.

GSK will also provide all of the study investigators with the full summary of the study results within one year of completion of the study. The investigators are encouraged to share the summary results with the study subjects, as appropriate.

Upon request, GSK will provide the investigator with the randomization codes for their site only after completion of the full statistical analysis.

A manuscript will be progressed for publication in the scientific literature if the results provide important scientific or medical knowledge.

GSK aims to post a results summary to the GSK Clinical Study Register and other publicly available registers no later than 8 months after the last subject's last visit (LSLV). For this study, the timing of such posting of a results summary would be after completion of Part B, or after Part A if a decision is made not to proceed with Part B. In addition, the aim is to submit a manuscript to a peer-reviewed journal for publication within 18 months of LSLV. GSK also aims to publish the full study protocol on the GSK Clinical Study Register at the time the results of the study are published as a manuscript in the scientific literature. For this study, the timing of such publication would be at the time the results of Part B are published as a manuscript in the scientific literature, or Part A if a decision is made not to proceed with Part B.

9.8. Independent Data Monitoring Committee (IDMC)

An IDMC will be utilized in this study to ensure external objective medical and/or statistical review of safety and/or efficacy issues in order to protect the ethical and safety interests of subjects and to protect the scientific validity of the study. The schedule of any planned interim analysis and the analysis plan for IDMC review is described in the charter, which is available upon request.

11. APPENDICES

11.1. Appendix 1: Highly Effective Methods For Avoiding Pregnancy In Females Of Childbearing Potential

The following is the all inclusive list of the highly effective methods for avoiding pregnancy (i.e., have a failure rate of less than 1% per year when used consistently and correctly and, when applicable, in accordance with the product label).

- Abstinence from penile-vaginal intercourse, when this is the preferred and usual lifestyle [[Hatcher, 2007a](#)].
- Oral contraceptive, either combined or progestogen alone [[Hatcher, 2007a](#)]
- Injectable progestogen [[Hatcher, 2007a](#)].
- Implants of etonogestrel or levonorgestrel [[Hatcher, 2007a](#)].
- Estrogenic vaginal ring [[Hatcher, 2007a](#)].
- Percutaneous contraceptive patches [[Hatcher, 2007a](#)].
- Intrauterine device (IUD) or intrauterine system (IUS) that meets the SOP effectiveness criteria as stated in the product label [[Hatcher, 2007a](#)].
- Male partner sterilization (vasectomy with documentation of azoospermia) prior to the **female subject's entry** into the study, and this male is the sole partner for that subject [[Hatcher, 2007a](#)]. The information on the male sterility can come from the site personnel's: review of subject's medical records; medical examination of the subject and/or semen analysis; or interview with the subject on his medical history.
- Male condom combined with a female diaphragm, either with or without a vaginal spermicide (foam, gel, film, cream, or suppository) [[Hatcher, 2007b](#)]
- Nonoxynol-9 is the critical component in most spermicides, and is regarded as an acceptable spermicidal agent. Concern has been raised that nonoxynol-9 damages the epithelial lining of the vagina, and exposure may facilitate transmission of viruses, particularly human immunodeficiency virus (HIV). The World Health Organization (WHO) conducted a technical consultation in October 2001 and concluded that the increased risk for such transmission was low to minimal [[World Health Organization. WHO/CONRAD, 2003](#)].

References

[figure not shown]

11.2. Appendix 2: Country Specific Requirements

No country-specific requirements exist.

11.3. Appendix 3: Liver Chemistry Stopping and Follow-up Criteria

Appendix3A: Baseline Liver Chemistries and Follow-up

[figure not shown]
Actions in the Case of Elevated Baseline Liver Chemistries (Discovered after Randomization)

Refer to flow diagram above.

1. If Baseline ALT or bilirubin meets the liver chemistry stopping criteria, hold IP. Refer to flow diagram above for appropriate followup of the subject.
2. If Baseline ALT is $\geq 2xULN$ or bilirubin is $> 1.5xULN$ but do not meet the liver chemistry stopping criteria, continue IP and obtain a repeat sample within 48 hours or at hospital discharge if earlier.
 - If the repeat ALT is $< 3xULN$, and bilirubin is $< 2xULN$ continue IP. Subsequent testing according to usual study schedule (Table 1).

- If the repeat ALT is $\geq 3xULN$ or bilirubin is $\geq 2xULN$ but do not meet liver chemistry stopping criteria, continue IP and monitor ALT and bilirubin as needed in accordance with [Appendix 3B](#) (below).
- If the repeat ALT and bilirubin results meet any of the liver chemistry stopping criteria, hold IP. Refer to flow diagram above for appropriate followup of the subject.

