Appendix 3B: Phase III-IV Liver Safety Algorithms

Note: This algorithm does not apply to liver chemistry abnormalities prior to any administration of investigational product, (where the results are not available pre-randomization). Refer to algorithm ([Appendix 3A](#)) for appropriate follow-up of those subjects.

Liver Chemistry Stopping Criteria

Phase III-IV liver chemistry stopping and follow up criteria have been designed to assure subject safety and evaluate liver event etiology (in alignment with the FDA premarketing clinical liver safety guidance).

Phase III-IV liver chemistry stopping criteria 1-7 are defined below and are presented graphically in the figure above:

1. ALT $\geq 3xULN$ and bilirubin $\geq 2xULN$ (>35% direct bilirubin) (or ALT $\geq 3xULN$ and INR > 1.5, if INR measured, (in any subject who is not receiving anti-coagulant therapy).

NOTE: if serum bilirubin fractionation is not immediately available, withdraw study drug for that subject if ALT ≥ 3 xULN and bilirubin ≥ 2 xULN. Serum bilirubin fractionation should be performed if testing is available. If testing is unavailable, **record presence of detectable urinary bilirubin on dipstick**, indicating direct bilirubin elevations and suggesting liver injury.

2. ALT ≥ 8 xULN.
3. ALT ≥ 5 xULN but < 8 xULN persists for ≥ 2 weeks
4. ALT ≥ 3 xULN but < 5 xULN persists for ≥ 4 weeks
5. ALT ≥ 3 xULN if associated with symptoms (new or worsening) believed to be related to hepatitis (such as fatigue, nausea, vomiting, right upper quadrant pain or tenderness, or jaundice) or hypersensitivity (such as fever, rash or eosinophilia).
6. ALT ≥ 5 xULN but < 8 xULN and cannot be monitored weekly for ≥ 2 weeks
7. ALT ≥ 3 xULN but < 5 xULN and cannot be monitored weekly for ≥ 4 weeks

When any of the liver chemistry stopping criteria 1-7 is met, refer to [Appendix3C](#) "Followup for Liver Chemistry Stopping Criteria 1-7".

Appendix3C: Followup for Liver Chemistry Stopping Criteria 1-7

- **Immediately** withdraw investigational product for that subject
- Report the event to TIMI Medical Hotline/GSK **within 24 hours** of learning its occurrence

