- Complete the liver event CRF and SAE data collection tool if the event also meets the criteria for an SAE. All events of ALT ≥ 3 xULN **and** bilirubin ≥ 2 xULN ($> 35\%$ director ALT ≥ 3 xULN and INR > 1.5 , if INR measured); INR measurement is not required and the threshold value stated will not apply to subjects receiving anticoagulants), termed 'Hy's Law', **must be reported as an SAE**. Note that baseline liver chemistries not available prior to randomization and start of IP and subsequently found to have ALT ≥ 3 xULN **and** bilirubin ≥ 2 xULN will not be reported as an SAE or considered to have met Hy's Law criteria.

NOTE: if serum bilirubin fractionation is not immediately available, withdraw study drug for that subject if ALT ≥ 3 xULN **and** bilirubin ≥ 2 xULN. Serum bilirubin fractionation should be performed if testing is available. If testing is unavailable, **record presence of detectable urinary bilirubin on dipstick**, indicating direct bilirubin elevations and suggesting liver injury.

- Complete the liver imaging and/or liver biopsy CRFs if these tests are performed
- Perform liver event follow up assessments, and monitor the subject until liver chemistries resolve, stabilize, or return to baseline values as described below.
- After completion of the liver chemistry monitoring, the subject should remain in the study until Week 24.

For subjects whose baseline liver chemistries not available at the time of randomisation are subsequently found to exceed GSK's Phase 3-4 liver chemistry stopping criteria, IP will be held. As per [Appendix 3A](#), if repeat liver chemistries up to 14 days in these subjects fall to within a defined criteria, IP can be restarted. For all other new abnormalities of liver chemistries that meet IP stopping criteria after randomization, do not restart IP. In addition, for criterion 1:

- Make every reasonable attempt to have subjects return to clinic within **24 hours** for repeat liver chemistries, liver event follow up assessments (see below), and close monitoring.
- A specialist hepatology consultation is recommended.
- Monitor subjects twice weekly until liver chemistries (ALT, AST, alkaline phosphatase, bilirubin) resolve, stabilize or return to within baseline values.

For criteria 2, 3, 4 and 5:

- Make every reasonable attempt to have subjects return to clinic **within 24–72 hrs** for repeat liver chemistries and liver event follow up assessments (see below).

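### For an on-drug repeat liver test that meets a stopping criterion, Appendix 3A says hold IP and Appendix 3C says withdraw it, and the text leaves restart unclear

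*Protocol*

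**What the plan says.** Protocol Sections 3.1.3 and 6.4.1 allow IP to be given before local liver results are available. Section 6.4.1 then points to Appendix 3A for a raised baseline discovered after randomization, and to Appendices 3B and 3C for the stopping criteria.

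- **Appendix 3A, item 1** covers a baseline that itself meets a stopping criterion: hold IP and follow the diagram.
- **Appendix 3A, item 2** covers a baseline at or above 2xULN for ALT, or above 1.5xULN for bilirubin, that meets no stopping criterion: "continue IP and obtain a repeat sample within 48 hours or at hospital discharge if earlier". Two of its sub-bullets matter here. For a repeat at or above 3xULN ALT or 2xULN bilirubin that meets no stopping criterion, the site is to "continue IP and monitor ALT and bilirubin as needed in accordance with" Appendix 3B. For a repeat that does meet one: "If the repeat ALT and bilirubin results meet any of the liver chemistry stopping criteria, hold IP". The next sentence is "Refer to flow diagram above for appropriate followup of the subject".
- **Appendix 3B, scope note:** "This algorithm does not apply to liver chemistry abnormalities prior to any administration of investigational product", where the results were not available before randomization; those subjects are sent to Appendix 3A. After listing the criteria it adds: "When any of the liver chemistry stopping criteria 1-7 is met, refer to" Appendix 3C.
- **Appendix 3C, first bullet:** immediately "withdraw investigational product for that subject". A later paragraph describes hold-and-restart, attributed to Appendix 3A, for subjects whose late-known baseline exceeded the stopping criteria, if repeats up to 14 days fall within defined limits. It then says: "For all other new abnormalities of liver chemistries that meet IP stopping criteria after randomization, do not restart IP".

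**The concern.** The repeat in Appendix 3A item 2 is drawn while the subject is taking IP, so a stopping-level value on it is a post-dose result. Appendix 3A nevertheless handles it with the same instruction and the same diagram as a pre-dose baseline, while the route through Appendices 3B and 3C treats it as an on-treatment stopping event. A site following one appendix would interrupt dosing. A site following the other would end it for good.

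Hepatotoxicity is the first risk listed in Section 1.2.2, which relies on the stopping criteria being well defined, and liver events are of special interest under Section 6.4.6. Section 3 allows no waivers apart from immediate safety concerns, so sites need one rule they can follow. At stake are consistent handling of a subject with a stopping-level liver result and consistent recording of it as an interruption (Section 5.1) or a permanent discontinuation (Section 4.4).

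The primary efficacy analysis is not the issue. Section 8.3.2 counts events after IP discontinuation, and follow-up runs to Week 24 either way.

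**Working it through.** No sample size, power or error rate is involved. The check takes one case through the three appendices.

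**Case (illustrative values).** Baseline ALT 2.5xULN with normal bilirubin, known only after the first dose. Repeat ALT 9xULN within 48 hours, on IP.

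**Step 1: classify the baseline.** 2.5 is at least 2, so Appendix 3A applies. Every one of criteria 1-7 requires ALT of at least 3xULN, and 2.5 is below 3, so none is met. The subject is in item 2, not item 1, and IP continues.

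**Step 2: classify the repeat.** 9 is at least 8, so criterion 2 is met.

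**Step 3: read off the instruction.**

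| Question | Appendix 3A, item 2 | Appendices 3B and 3C |
|---|---|---|
| Does it cover this result? | Yes, third sub-bullet | Yes: only abnormalities before any IP are exempt, and IP has been given |
| Action on IP | Hold | Withdraw immediately |
| Follow-up | Baseline flow diagram | Appendix 3C follow-up for criteria 1-7 |
| Restart | Not stated in the text; depends on the diagram | Exception does not apply, since the baseline did not exceed the criteria; no restart if the result counts as *new* |

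**Step 4: can the branch occur?** Yes. Criteria 1, 2, 5, 6 and 7 can be met at a 48-hour repeat. Criteria 3 and 4 cannot be newly met then, because they need 2 and 4 weeks of persistence.

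**Step 5: where readings can diverge.** The Appendix 3B note can be read as moving the subject to Appendix 3A for the whole work-up, or as exempting only the pre-dose value. In Appendix 3C, *new* is not defined for a value that rises from an already raised baseline. Appendix 3A also sends the milder repeat, below the stopping criteria, to Appendix 3B but keeps the more serious one under its own diagram.

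**Step 6: could the diagram settle it?** There are three possibilities:

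- If it allows restart on this branch, it conflicts with the Appendix 3C rule for all other new abnormalities, provided the repeat counts as one.
- If it forbids restart, the restart question is settled, but the hold and withdraw wording still differs.
- If it sends the subject to Appendix 3C, practice is aligned and only the wording of the sub-bullet needs correcting.

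In each case at least the text of the sub-bullet needs to be reconciled.

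**The case against.** The strongest reply is that the text can be read as consistent. Both instructions stop dosing at once. The only written permission to restart belongs to subjects whose baseline exceeded the criteria, and the example subject is not one of them. The sentence that follows would then bar restart, and the diagram may say so. Section 6.4.11 also requires contact with the sponsor or hotline at the onset of liver elevations, and Section 5.1 requires consultation before resuming IP where there is a potential safety concern, so unnoticed re-exposure is less likely.

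Much of this stands. A reader might infer that Appendix 3A permits restart here, so that the two appendices give opposite orders on re-exposure. No visible sentence says that: a hold is not permission to resume, and the diagram's absence from the text reviewed is not a fault in the plan.

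A reader might also infer that the appendices split on reporting such a result as a Hy's Law case. They do not. The exemption in Appendix 3C names only baseline chemistries, Appendix 3A says nothing on SAE reporting, and Sections 6.4.4.2 and 6.4.11 require on-drug cases to be reported as SAEs within 24 hours.

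What the reply does not remove is that the consistent reading has to be assembled by the site. It must treat *hold* as *withdraw*, take the Appendix 3B exemption as applying to the result and not to the subject, and decide that a worsening value is *new*. The hotline safeguard makes a poor outcome less likely, but it does not replace a single written instruction.

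**Conclusion.** The point holds as a conflict of wording with a safety consequence. For a post-dose repeat that meets a stopping criterion, after a baseline that was raised but below the criteria, Appendix 3A says hold and the route through Appendices 3B and 3C says withdraw. Restart on this branch is unclear in the text; it is not shown to be permitted.

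The number affected is expected to be small, because a subject must have a late-known baseline, a value in a limited range, and a repeat that reaches a stopping criterion within about 48 hours. That is a judgement. The protocol gives no rate for any of these steps, so no count is offered and no effect on the trial's overall hepatic conclusion is claimed.

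The conclusion rests on the written text alone. The diagram could settle the restart question but would not by itself align the two written instructions. No view is taken on which instruction is clinically right.

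**What to change.** Reconcile four places in Section 11.3: the third sub-bullet of Appendix 3A item 2, the Appendix 3A flow diagram, the scope note at the start of Appendix 3B, and the withdrawal and restart text of Appendix 3C. After the change, a post-dose repeat that meets a stopping criterion should have one stated action and one stated restart status wherever it appears.

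The scope note should say whether the exemption attaches to the pre-dose result or to the subject. Appendix 3C should say whether a value that worsens from a raised baseline counts as a new abnormality. The sponsor decides which rule applies. The Hy's Law reporting text needs no change for this point.

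The cost is a short wording amendment and a matching update to the site manual, with no added tests or visits.
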